## 1. Study Design and Background Information

### 1.1 Target Disease and Treatment Methods

Amyotrophic lateral sclerosis (ALS) is characterized by selective and progressive degeneration and the death of primary (upper) and secondary (lower) motor neurons. The pathogenesis of ALS remains largely unknown. The symptoms of ALS mainly include muscle weakness or stiffness. The progression of ALS is accompanied by upper limb dysfunction, gait disturbance, dyslalia, dysphagia, and respiratory disorder, but not by sensory disturbance or dysuria. Due to the relatively rapid progression of the disease, average survival is about 2 to 4 years without ventilator use. Motor neuron death is likely to be associated with excitatory amino acids, free radicals, and viral infection.

Riluzole (brand name: Rilutek 50 mg tablets), a glutamic acid antagonist, and edaravone (product name: Radicut® Injection 30 mg), a free radical scavenger, have been approved as therapeutic drugs for ALS.

### 1.2 Name and Description of the Investigational Drug

Edaravone is a free radical scavenger developed by Mitsubishi Tanabe Pharma Corporation (sponsor) as a neuroprotective agent.

Radicut® (edaravone injection) was first approved in Japan in 2001 as a therapeutic drug for the acute phase of cerebral infarction. Usually, 30 mg of Radicut® is intravenously (IV) administered over 30 minutes twice per day. The duration of administration should be within 14 days. Based on a series of clinical studies in ALS patients in Japan, Radicut® was also approved for ALS treatment in Japan in June 2015, in South Korea in December 2015, and in the United States in May 2017. For ALS treatment, 60 mg of Radicut® is IV administered over 60 minutes once per day. The first cycle consists of 14 consecutive days followed by a 14-day washout period. Subsequent cycles consist of daily dosing for 10 days out of 14-day periods, followed by 14-day washout periods.

As described above, Radicut® (edaravone injection) has been used for ALS treatment. Nevertheless, IV infusion places a large burden on patients; therefore, there is a need for more convenient oral agents.

### 1.3 Results of Non-clinical and Clinical Studies

#### 1.3.1 Non-clinical Studies

An *in vitro* assay showed that edaravone had a radical scavenging effect, lipid peroxidation inhibitory effect, and vascular endothelial cell injury inhibitory effect. An *in vivo* assay showed that IV edaravone administration to cerebral ischemic animals (rats) yielded a cerebral edema inhibitory effect, tissue injury protection effect, neurological symptom improvement effect, and delayed neuronal death inhibitory effect. In female mutant SOD transgenic rats, a reduction of the inclined plate angle was inhibited in the inclined plate test. In a canine subarachnoid hemorrhage model, edaravone displayed a cerebral vasospasm inhibitory

effect. In the safety pharmacology studies, a transient decrease in blood pressure was observed at doses higher than the therapeutic dose; however, this will pose no significant concerns in clinical settings.

In the toxicity studies, the no observed adverse effect level (NOAEL) for multiple doses of rapid IV injection was 10 mg/kg/day in rats and 30 mg/kg/day in dogs. As the major toxicological changes, transient blinking and lacrimation immediately after administration and reduced body weight gain and a decrease in food consumption were observed at the minimum toxic dose in rats; however, these changes were relieved or disappeared after withdrawal from the drug. In dogs, salivation, sedation, blinking, sneezing, and hind limb weakness were observed in a transient manner.

In a 2-week multiple oral dose study, the NOAEL was 300 mg/kg/day in rats, 30 mg/kg/day in female dogs, and 100 mg/kg/day in male dogs. In rats, toxicological changes were observed only in the 1,000 mg/kg/day group, and were similar to those seen after rapid IV injection. Forestomach erosion, prolonged activated partial thromboplastin time, and submandibular gland acinar cell hypertrophy were observed as toxicological changes after an oral dose but not after rapid IV injection. In dogs, toxicological changes were observed in females in the  $\geq 100$  mg/kg/day groups and males in the 300 mg/kg/day group, and were similar to those seen after rapid IV injection.

At the NOAEL, there were no findings of clinical importance in other toxicity studies, as well.

The PK assessment in rats showed that the dose correlated well with  $C_{max}$  and AUC. The major metabolites were glucuronide conjugate and sulfate conjugate, which were excreted in the urine. The urinary excretion of the unchanged drug was approximately 1% of the dose. Regarding the sulfate conjugate and glucuronide conjugate, neither a radical scavenging effect nor a lipid peroxidation inhibitory effect have been observed.

In an *in vitro* assay using human kidney homogenates, after deconjugation of the sulfate conjugate, the product was reconjugated with glucuronic acid and excreted mainly as the glucuronide conjugate in the urine. The glucuronidation reaction involved multiple uridine diphosphate glucuronyl transferases (UGTs), including UGT1A9. The effects of edaravone and its metabolites in inhibiting CYPs, UGTs, and transporters and inducing CYPs were not clinically significant. Edaravone was bound to human serum proteins at a rate of 91% to 92% (primarily to albumin).

### 1.3.2 Clinical Study Results

The clinical study results of Radicut® (non-proprietary name: edaravone) injection are presented below.

Thus far, the following clinical studies have been performed: 5 clinical pharmacology studies in healthy adult subjects in Japan and Europe; 8 clinical studies in acute cerebral infarction patients in Japan, Europe, and South Korea, 3 clinical studies 3 in subarachnoid hemorrhage patients in Japan; and, 5 clinical studies in ALS patients in Japan.

In the clinical pharmacology study, Japanese healthy adult male subjects were given a single dose (0.2–2.0 mg/kg) or multiple doses (1.0 mg/kg/day for 7 days) of IV infusion over a period of 40 minutes or 3 hours to assess safety and the PK profile. After the single dose,

abnormal laboratory changes were observed in 2 subjects; however, values had returned to within the normal range at the end-of-study assessment, indicating no safety concerns. The highest levels of exposure to the unchanged drug in plasma were 3,061 ng/mL for  $C_{max}$  (1.5 mg/kg) and 3,005 ng•hr/mL for  $AUC_{0-24hr}$  (1.5 mg/kg). The  $C_{max}$  and  $AUC_{0-24hr}$  showed a proportional increase with dose. The elimination half-life and urinary excretion were nearly stable, regardless of the dose. No particular changes were observed in the PK profile after the single and multiple doses.

In the clinical pharmacology study outside Japan, Caucasian healthy adult male and female subjects were given rapid IV edaravone injection (0.05–0.2 mg/kg) followed by 24-hour continuous IV infusion (0.125–0.5 mg/kg/hr) to assess safety and the PK profile. The commonly observed AEs were infusion site pain, diarrhoea, and headache; however, they were also seen in the placebo group, and resolved prior to the end of the observation. The highest dose group (0.2 mg/kg + 0.50 mg/kg/hr) displayed a plasma unchanged drug exposure of 1,164.7 ng/mL for  $C_{max}$  and 22,455.6 ng•hr/mL for  $AUC_{0-24hr}$ .

Japanese healthy elderly subjects and healthy adult male subjects received multiple doses (0.5 mg/kg, twice daily for 2 days), and the PK and safety were evaluated. Following multiple doses of 30-minute IV infusion, the PK of the unchanged drug and the metabolites in plasma were similar for the elderly subjects and adult male subjects, and no particular changes were observed in the urinary excretion. No particular differences were found in safety between the elderly and adult male subjects. In addition, no clinically significant findings were observed.

The population PK analysis was performed using the PK data from the 5 clinical pharmacology studies of IV edaravone administration to healthy adult subjects in Japan and Europe. As a result, no particular changes were observed in the PK profiles between Japanese and Caucasian by race, sex, age, or body weight. Following IV edaravone infusion to ALS patients at the approved dose of 60 mg/60 min, the calculated  $C_{max}$  and  $AUC_{0-\infty}$  were 1,049 ng/mL and 1,374 ng•hr/mL, respectively.[1]

#### 1.4 Study Plan

This study was planned to examine the pharmacokinetics (PK), safety, and tolerability of oral administration of edaravone.

## 2. Study Objectives

### Primary objective:

To evaluate the PK, safety, and tolerability of single and multiple doses of edaravone solution and suspension in healthy adult males.

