#### Comparator:

##### 1) Comparator to the solution

For Cohort S1, dissolve polyvinyl alcohol (Japanese Pharmaceutical Excipient) in purified water, and use the mixture as an oral solution.

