##### 2) Comparator to the suspension

Suspend crystalline cellulose powder in polyvinyl alcohol (Japanese Pharmaceutical Excipient) or in a mixture of polyvinyl alcohol (Japanese Pharmaceutical Excipient) and xanthan gum (Japanese Pharmaceutical Excipient), and use the mixture as an oral suspension.

- Cohorts S2, S3, S5, S6, S7, M1, and M2: Polyvinyl alcohol
- Cohort S4: Polyvinyl alcohol and xanthan gum

If the dosage form of the investigational drug (solution or suspension) is changed, the same dosage form will be used for the comparator.

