##### (1) Part 1 (single-dose study)

A single oral dose of the study drug will be given to subjects under fasting conditions in the morning or 30 minutes after breakfast. In Cohort S3-2, subjects in Cohort S3-1 will be given the same study drug that is allocated in Cohort S3-1 in a single oral dose after at least a 4-day washout period. Doses of Cohort S2 and thereafter are tentative. Based on the PK data obtained up to 24 hours post-dose and the safety data obtained up to 48 hours post-dose of the previous cohort, the sponsor and a medical expert will examine and determine the dose with the agreement of the investigator, such that the exposure of the minimum toxic dose (10,226 ng/mL for  $C_{max}$  and 1,226 ng•hr/mL for  $AUC_{0-24hr}$  in a free base form) is not exceeded. However, the highest dose in Part 1 shall not exceed 7,200 mg. The common ratio between the dose and the estimated mean  $C_{max}$  and  $AUC_{0-24hr}$  should be  $\leq 5$  between successive cohorts.

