The estimated PK parameters of oral edaravone in humans at the initial dose of 60 mg and the planned highest dose of 3,600 mg are as follows: 93 ng/mL for  $C_{max}$  and 202 ng•hr/mL for  $AUC_{0-24hr}$  at 60 mg (8 ng/mL for  $C_{max}$  and 16 ng•hr/mL for  $AUC_{0-24hr}$  in a free base form) and 5,577 ng/mL for  $C_{max}$  and 12,110 ng•hr/mL for  $AUC_{0-24hr}$  at 3,600 mg (452 ng/mL for  $C_{max}$  and 981 ng•hr/mL for  $AUC_{0-24hr}$  in a free base form).

Based on findings from the non-clinical studies, the estimated AEs are sedation, decreased blood pressure, and increased heart rate, which were transient in the studies. By observing the subjects' clinical symptoms and vital signs during the study period, it was determined to be feasible to conduct this study.

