Descriptive statistics will be calculated for 12-lead ECG data, for each timepoint. Data outside of the reference range will be indicated via an attached flag in the list.

(3) Pharmacokinetics

For the plasma concentrations of unchanged edaravone, sulfate conjugate, and glucuronide conjugate, descriptive statistics will be calculated by dose for each time point and time after dosing. In addition, descriptive statistics will be calculated for the PK parameters (e.g.,  $C_{max}$ ,  $t_{max}$ , AUC, and  $t_{1/2}$ ) of unchanged edaravone, sulfate conjugate, and glucuronide conjugate by dose.

- Dose proportionality will be assessed using the  $C_{max}$ ,  $AUC_{0-\text{last}}$ , and  $AUC_{0-\infty}$  (except for Cohort S3-2) of unchanged edaravone, sulfate conjugate, and glucuronide conjugate collected in Part 1, using a power model. In addition, the linearity will be evaluated using a lack-of-fit test.
- The effect of food on the PK parameters of edaravone will be assessed using the  $C_{max}$ ,  $AUC_{0-\text{last}}$ , and  $AUC_{0-\infty}$  of unchanged edaravone, sulfate conjugate, and glucuronide conjugate in Cohorts S3-1 and S3-2. The geometric mean ratio (fed/fasting conditions) and the 90% confidence interval will be calculated via analysis of variance, using the data after log transformation under fed and fasting conditions and the subjects as factors.
- The ratio of the  $C_{trough}$  (plasma concentration at the end of the dosing interval) of unchanged edaravone, sulfate conjugate, and glucuronide conjugate for each day of dosing to those after the last dose will be calculated for each subject in Part 2, and the geometric mean and 95% confidence interval will also be calculated.
- The linearity factor (LF) will be calculated to assess the linearity of unchanged edaravone, sulfate conjugate, and glucuronide conjugate after multiple doses in Part 2.

$LF = AUC_{0-T} \text{ (last dose)} / AUC_{0-\infty} \text{ (first dose)}$

T: Dosing interval

- The ratio of accumulation (RA) will be calculated to assess the accumulation of unchanged edaravone, sulfate conjugate, and glucuronide conjugate after multiple doses in Part 2.

$RA = AUC_{0-T} \text{ (last dose)} / AUC_{0-T} \text{ (first dose)}$

T: Dosing interval

(4) Pharmacodynamic assessment

For PD assessments, the Statistical Analysis Plan and report will be prepared separately.

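### The primary objective covers multiple doses of solution that no cohort is planned to receive, and the pooled dose-proportionality fit confounds dosage form with the lowest dose

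*Protocol*

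**What the plan says.** The primary objective (Protocol Section 2, repeated in the Protocol Summary) is "To evaluate the PK, safety, and tolerability of single and multiple doses of edaravone solution and suspension in healthy adult males".

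Section 7.1 assigns the dosage forms through the comparator text. Under the comparator to the solution it names one cohort only: "For Cohort S1, dissolve polyvinyl alcohol (Japanese Pharmaceutical Excipient) in purified water, and use the mixture as an oral solution". Under the comparator to the suspension it lists "Cohorts S2, S3, S5, S6, S7, M1, and M2: Polyvinyl alcohol" and "Cohort S4: Polyvinyl alcohol and xanthan gum". It adds: "If the dosage form of the investigational drug (solution or suspension) is changed, the same dosage form will be used for the comparator". Section 5.3.1 requires drug and comparator to look alike within each form, so the comparator's form shows the form of the active drug.

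Table 1 in Section 8.3.1 gives S1 as a single 60 mg dose. Table 2 gives M1 and M2 as the only multiple-dose cohorts. The dosing text in Section 8.3.1 says "Doses of Cohort S2 and thereafter are tentative", so only the S1 dose is fixed.

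Section 13.4(3) opens the relevant bullet with "Dose proportionality will be assessed using the" and names Cmax, AUC to the last sample and AUC to infinity from Part 1. The method is a power model, S3-2 is the only excluded cohort, and a lack-of-fit test is added for linearity. The section names no dosage-form term.

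**The concern.** Two things do not fit together. First, the objective pairs both dosing patterns with both forms, but one of the four combinations, multiple doses of solution, has no planned cohort.

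Second, the power model keeps out the fed data of S3-2 but leaves in the only solution cohort, which also sits at the lowest dose. No suspension cohort is planned at 60 mg, so the data cannot separate an effect of form from an effect of dose at that end. A solution needs no dissolution step, so a difference in availability is possible, and the secondary objectives themselves list dissolution profile as a factor in the PK. Any such difference would enter the slope. A suspension that is exactly proportional could then look less (or more) than proportional.

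**Working it through.** **Forms against objective.** Single-dose solution: S1. Single-dose suspension: S2, S3-1, S3-2, S4, S5, S6, S7. Multiple-dose suspension: M1, M2. Multiple-dose solution: none.

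**Inputs from the Protocol.** The tentative doses in the fit are 60, 240, 800 (S3-1), 1,600, 2,400, 3,600 and 800 mg (S7), with 6 active subjects per cohort (Section 6.1), so 42 in all. Section 6.1 states that the sample size has no power calculation. The Protocol gives no between-subject CV and no solution/suspension exposure ratio, so both are assumed below.

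**Model.** ln(PK) = a + b ln(dose), where b = 1 means proportional.

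**Share of slope information.**
- The ln doses are 4.094, 5.481, 6.685, 7.378, 7.783, 8.189 and 6.685, with mean 6.613.
- The squared deviations are 6.346, 1.283, 0.005, 0.584, 1.368, 2.482 and 0.005, with sum 12.073. Times 6 subjects, Sxx = 72.4.
- S1's share is 6.346/12.073 = 52.6%. Without S7, without S4, or without both it is 52.1%, 50.2% or 48.8%.
- The share moves with the doses chosen. By the same formula, S6 at the 7,200 mg cap gives 46.7%, and S5 and S6 both held at 1,600 mg give 59.9%.

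**Shift in the slope.** Let r be suspension availability divided by solution availability, and let the suspension be truly proportional (b = 1). S1 then lies ln(1/r) above the suspension line. The fitted slope is 1 + (−2.519/12.073) × ln(1/r) = 1 − 0.209 × ln(1/r).

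| assumed r | fitted slope |
|---|---|
| 1.0 | 1.00 |
| 0.9 | 0.978 |
| 0.8 | 0.953 |
| 0.7 | 0.926 |
| 0.6 | 0.893 |

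If the suspension were the more available form, the shift would be upward. At r = 1.25 the slope is 1.047.

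**Precision.** The half-width of a 90% interval is t × s/√Sxx, with s = √ln(1 + CV²).
- All seven cohorts (40 df, t = 1.684): at CV 30%, 1.684 × 0.294/√72.4 = 0.058. At CV 40%, 1.684 × 0.385/√72.4 = 0.076.
- S1 left out: mean ln dose 7.033, Sxx = 28.0, which is 38.7% of 72.4. With 34 df and t = 1.691, the half-width is 0.094 at CV 30% and 0.123 at CV 40%. The standard error rises by √(72.4/28.0) = 1.61. The dose range falls from 3,600/60 = 60-fold to 3,600/240 = 15-fold.

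**Does the lack-of-fit test guard against this?** S1's cohort leverage is 1/7 + 0.526 = 0.67, so the line absorbs two thirds of a shift in S1. The noncentrality is 6 × (1 − 0.668) × [ln(1/r)]²/s². At r = 0.8 and CV 30% that is about 1.15. There are six distinct doses, so the test has 4 and 36 df. At an assumed 5% level its power is about 11% (r = 0.8) and 21% (r = 0.7) at CV 30%, and about 8% and 14% at CV 40%.

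**The case against.** The objective can be read collectively: single and multiple doses, across the two forms used. On that reading the design delivers it. Section 7.1 also allows the dosage form to change without tying this to a cohort. Both points are fair, and they make the first part a matter of wording. They do not create a planned multiple-dose solution cohort.

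A reader might infer that the design fails because it cannot compare solution with suspension. No objective promises that comparison. The form-specific secondary aims concern a single dose of suspension.

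A reader might also infer that the slope is biased. The Protocol does not say that the forms differ in availability. If r is near 1 there is no shift, so the bias is conditional.

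On consequences, Section 13.4(3) sets no acceptance range for the slope. Sections 8.3.1 and 8.4 choose doses from observed concentrations, Cmax, AUC and safety, not from the power model. The harm is therefore to interpretation only.

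The objection also has force against making the suspension-only fit the main one. At CV 40% the standard errors are 0.045 pooled and 0.073 without S1. The pooled slope has the smaller mean squared error while its bias stays below √(0.073² − 0.045²) ≈ 0.057, which means r above about exp(−0.057/0.209) = 0.76. Without S1, moreover, S2 alone holds 1.553²/4.670 = 51.6% of the remaining information. The suspension-only fit also still mixes S4's xanthan gum vehicle and S7's Caucasian subjects.

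Finally, Section 13.1 leaves detail to an SAP that is not at hand, and a fit without S1 could be there. The pooling itself is fixed in the Protocol, however, because Section 13.4(3) names the one cohort to leave out.

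**Conclusion.** The point holds as a minor one, in two parts.

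The wording of the primary objective reaches further than the planned cohorts, since multiple doses of solution are not planned. This does not show that the trial misses its purpose, or that a multiple-dose solution result would be claimed. The dose tables and form lists by cohort make clear what was given.

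In the power model, dosage form is fully confounded with the lowest dose, and that dose supplies about half of the slope information (53% at the tentative doses). If availability differs by 20% to 30%, the slope moves by about 0.05 to 0.07. That is comparable to the 90% half-width of 0.06 to 0.08, and the lack-of-fit test would usually miss it. These figures rest on the tentative doses, 6 evaluable active subjects per cohort, assumed CVs of 30% to 40% and an assumed availability ratio. The Protocol supports neither the claim that the slope is in fact biased nor any effect on dose selection.

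**What to change.** Reword the primary objective, in Section 2 and in the Protocol Summary, to single doses of solution and suspension and multiple doses of suspension.

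In Section 13.4(3), keep the pooled power model, labelled as mixing dosage forms. Add a pre-specified fit on the suspension cohorts only, with S1 left out, and report both. State that a departure from slope 1 seen only in the pooled fit will not be read as non-proportionality of the suspension.

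The cost is a few sentences and one extra fit. That fit is less precise: its 90% interval is about 1.6 times wider (half-width 0.12 against 0.08 at CV 40%), over a 15-fold rather than a 60-fold dose range. This is why it belongs beside the pooled fit and should not replace it.

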### Secondary objectives:

- To confirm the PK profiles of a single dose of edaravone suspension in different races, fed/fasted conditions, and different drug dissolution profiles.
- To collect ECG data to evaluate QTcF prolongation and proarrhythmic potential for edaravone.

### 3. Subjects

#### 3.1 Inclusion Criteria

Subjects who meet all of the following criteria will be enrolled in the study.

- (1) Healthy adult male volunteers
- (2) Japanese or Caucasian
- (3) Subjects aged between 20 and 45 years at the time of informed consent
- (4) Subjects who have thoroughly understood the contents of the study and voluntarily provided written informed consent to participate in the study

[Rationales for setting]

- (1) To examine the PK, safety, and tolerability in healthy adults.
- (2) To compare the PK between Japanese and Caucasians.
- (3) An age of  $\geq 20$  years was set to assure the legal capacity to give consent, and an age of  $\leq 45$  years was set to avoid excessive demographic variations.
- (4) To observe the provisions for subject protection in the Guidelines for Good Clinical Practice (GCP).

#### 3.2 Exclusion Criteria

Subjects who meet any of the following criteria between screening and study drug administration will be excluded from the study.

- (1) Subjects with a current or previous history of cardiac, hepatic, renal, gastrointestinal, respiratory, psychiatric, nervous, hematopoietic, or endocrine diseases, and those whom the investigator (or subinvestigator) deems unsuitable for the study
- (2) History of drug or food allergy
- (3) History of alcohol or drug abuse or dependence
- (4) Body mass index (BMI) of  $<18.0$  or  $>30.0$ , or body weight of  $<50$  kg  
(BMI formula: body weight [kg]/height [m], rounded to one decimal place)
- (5) Positive test for any of the following at screening: Hepatitis B surface antigen, serological test for syphilis, hepatitis C virus antibody, or human immunodeficiency virus antigen/antibody
- (6) Any clinically significant 12-lead ECG abnormalities, or QTc interval  $\geq 450$  msec
- (7) Blood donation or sampling with a total volume of  $\geq 400$  mL within 12 weeks,  $\geq 200$  mL within 4 weeks, or  $\geq 800$  mL within a year before providing informed consent
- (8) Blood component donation or blood sampling within 2 weeks before providing informed consent
- (9) Subjects who have undergone any surgery known to affect the gastrointestinal absorption of drugs
- (10) Subjects who do not agree to use an effective method of contraception from initiation of the study drug administration to 14 days after completion (discontinuation) of study drug administration
- (11) Subjects who have previously received edaravone

- (12) Subjects who have participated in another clinical study and received a study drug within 12 weeks before providing informed consent
- (13) Use of any drug(s) other than the study drug within 7 days before initiation of study drug administration
- (14) Subjects judged by the investigator (or subinvestigator) to be unsuitable for the study for any other reason

[Rationales for setting]

- (1) To ensure the safety of subjects and to exclude unhealthy subjects.
- (2) To perform the study safely and ethically.
- (3) To perform the study safely and ethically.
- (4) To reduce PK variability due to BMI differences.
- (5) To perform the study safely and ethically.
- (6) To perform the study safely and ethically.
- (7) With reference to the "Enforcement Regulations for the Act on Securing a Stable Supply of Safe Blood Products," blood collection volumes and intervals are specified to ensure subject safety.
- (8) With reference to the "Enforcement Regulations for the Act on Securing a Stable Supply of Safe Blood Products," the blood collection interval was specified to ensure subject safety.
- (9) To avoid a possible effect on the PK.
- (10) To assure subject safety, even though there were no toxicity findings at the highest dose of 200 mg/kg in the reproductive and developmental toxicity studies.
- (11) Because this may affect the assessment of this study.
- (12) To perform the study ethically and to avoid any unpredictable effects of drugs whose efficacy and safety have not been established.
- (13) Because this may affect the PK of the investigational drug.
- (14) To perform the study safely and ethically.

